#### ***5.3.5.2 Contraceptive Guidelines for Female Subjects***

A female enrolling in this study must meet ONE of the following contraceptive criteria:

1. Is postmenopausal  
A postmenopausal state is defined as no menses for at least 1 year without an alternative medical cause. A high FSH level in the postmenopausal range may be used to confirm a postmenopausal state in women not using hormonal contraception or hormonal replacement therapy. However, a single FSH measurement is insufficient to establish a postmenopausal state without at least 1 year of amenorrhea.
2. Is premenopausal but has documentation of one of the following:
  - a. Hysterectomy
  - b. Bilateral salpingectomy
  - c. Bilateral oophorectomy

3. Has only 1 male sexual partner, that partner is vasectomized, and the absence of sperm has been confirmed
4. Is sexually abstinent from penile-vaginal intercourse as her usual and preferred lifestyle (abstinent on a long-term and persistent basis) and agrees to remain abstinent throughout the duration of the study
5. Agrees to use one of the following highly effective contraceptive methods for the duration of the study:
  - a. Combined hormonal contraception (containing estrogen and progestogen): oral, intravaginal, or transdermal
  - b. Progestogen-only hormonal contraception: oral, injectable, or implantable IUD or IUS
  - c. Bilateral tubal occlusion

#### **5.4 Screen Failures**

Screen failures are defined as participants who consent to participate but are not subsequently enrolled in the study. A minimal set of screen failure information is required to ensure transparent reporting of screen failure participants to meet the Consolidated Standards of Reporting Trials (CONSORT) publishing requirements and to respond to queries from regulatory authorities. Minimal information includes demography, screen failure details, and eligibility criteria.

Individuals who do not meet the following criteria for participation in the study may be rescreened according to the following guidelines after consultation with the Sponsor's Medical Monitor:

- Individuals who do not meet the screening 17-OHP inclusion criterion may be rescreened after 30 days if their glucocorticoid replacement dose is reduced for clinical reasons. Any morning dose of glucocorticoid medication should be taken after the screening blood draw to allow for an unimpeded assessment of 17-OHP.
- Individuals on incompatible or excluded concomitant medications may be rescreened after an appropriate washout period (e.g., 30 days or 5 half-lives, whichever is longer).

## 6 STUDY INTERVENTION

### 6.1 Study Intervention Administration

#### 6.1.1 Study Intervention Description

SPR001 is a small-molecule CRF1 receptor antagonist.

Details about the physical, chemical, and pharmaceutical properties of SPR001 are provided in the IB.

#### 6.1.2 Dosing and Administration

Initial subjects who enroll in this study will be treated with oral study drug at 400 mg QD at 10pm for 12 weeks. This dose is within the range of doses that were well tolerated and reduced key hormones (ACTH, 17-OHP, and androstenedione) in subjects with CAH in Cohort A of Study SPR001-201. For subjects who enroll later on in this study, the dose strength may be increased or decreased (by no more than 2-fold) and/or the dose regimen may be adjusted (e.g., to BID dosing, a regimen being tested in Study SPR001-201). In general, subjects are expected to complete the study at the dose strength and on the dose regimen at which they started the study, unless they experience a clinically significant AE that would warrant a dose reduction. An SRC will review the available safety, PK, and PD data from Study SPR001-201 Cohorts B/C/D and from this study on an ongoing basis and provide recommendations to the Sponsor, who will ultimately decide on any dosing adjustments in this study.

Only authorized site staff may dispense study drug. Sites will provide subjects with dosing instructions. Subjects being treated with study drug at 400 mg QD will be instructed to take 2 capsules daily at 10pm. If dosing is adjusted to a BID regimen, subjects will be instructed on when to take study drug in the morning and in the evening. If a subject goes to bed earlier than 10pm, the subject will take the 10pm dose of study drug at bedtime. Study drug will be taken with a meal or 5 to 15 minutes after consumption of a standardized snack. If a morning dose of study drug is added and a subject wishes to take his/her morning dose of study drug with breakfast, the Investigator should discuss the specific dosing situation with the Sponsor's Medical Monitor. If a morning dose of study drug is added, subjects should hold off on taking their morning dose of study drug on the mornings of all applicable study visits until after laboratory assessments have been completed. On all other days during the treatment period, subjects should take their morning dose of study drug at their usual time.

Instructions for concomitant glucocorticoid medication dosing are provided in [Section 6.5.1](#). Instructions for study drug dose reduction are provided in [Section 7.1](#). Criteria for study drug discontinuation are provided in [Section 7.2](#).

## **6.2 Preparation/Handling/Storage/Accountability**

### **6.2.1 Acquisition and Accountability**

The Investigator is responsible for study drug receipt and accountability, reconciliation, and record maintenance.

### **6.2.2 Formulation, Appearance, Packaging, and Labeling**

The drug product SPR001 is formulated as a white, hard-gelatin capsule containing either 50 mg or 200 mg of the drug substance SPN001 in powder form with no excipients.

Study drug capsules containing 50 mg SPN001 are size 4 and will be packaged with 32 capsules per bottle in a 30-mL high-density polyethylene (HDPE) bottle with a 28-mm child-resistant cap and an induction foil seal.

Study drug capsules containing 200 mg SPN001 are size 1 and will be packaged with either 14 capsules per bottle (in a 30-mL HDPE bottle with a 28-mm child-resistant cap and an induction foil seal) or with 60 capsules per bottle (in a 75-mL HDPE bottle with a 33-mm child-resistant cap and an induction foil seal).

Each bottle will be labeled in English with the protocol number, recommended storage conditions, name and address of the Sponsor, an Investigational Use Statement (“Caution: New Drug – Limited by Federal [USA] Law to Investigational Use”), and the instruction that the agent should be kept out of reach of children. Labeling will comply with all legal requirements and supply no information about individual subjects.

### **6.2.3 Product Storage and Stability**

Study drug capsules are stable when stored at room temperature (20 °C to 25 °C) but should be protected from light. Study drug must be stored in a secure, environmentally controlled area that is monitored (manually or automatically) and accessible only to the Investigator and authorized site staff.

## **6.3 Treatment Assignment**

Initial subjects who enroll in this study will be treated with study drug at 400 mg QD. This dose strength and/or dose regimen may be adjusted for subjects who enroll later on in this study based on ongoing review of the available safety, PK, and PD data from Study SPR001-201 Cohorts B/C/D and from this study by an SRC.

## **6.4 Study Intervention Compliance**

Subject compliance will be assessed by maintaining adequate study drug dispensing records. Subjects will return bottles of study drug at each visit for a pill count. The Investigator is responsible for ensuring that dosing is administered in compliance with the protocol.

## 6.5 Concomitant Therapy

Concomitant medication is any medication (including over-the-counter [OTC] medication, prescription medication, vaccines, vitamins, and supplements) that the subject is receiving at screening or receives during the study. Concomitant medications must be recorded, along with:

- Reason for use
- Dates of administration, including start and end dates
- Dosage information, including dose and frequency

All concomitant medications should be compared against the list of prohibited medications and the list of other medications of concern provided in [Section 12.1](#). Subjects should be instructed to contact the site immediately any time a new medication is required during the course of the study, including prescription and OTC medications, even those to be used for only a short period of time (e.g., antibiotics, cold and flu remedies, gastrointestinal therapies, opioids or other pain relievers). The Medical Monitor should be contacted if there are any questions regarding concomitant or prior therapy.

### 6.5.1 Glucocorticoid Replacement Therapy

Subjects must be on a stable regimen of glucocorticoid replacement therapy for  $\geq 12$  weeks before baseline to be eligible for this study. Changes in glucocorticoid dosing during the study are discouraged, and any changes will be recorded.

On the mornings of all study visits, including screening, subjects should hold off on taking any morning dose of glucocorticoid medication until after laboratory assessments are completed. On all other days during the study, subjects may take any morning glucocorticoid medication at their usual time.

### 6.5.2 Prohibited Concomitant Medications and Concomitant Medications of Concern

[Section 12.1](#) outlines medications that are either prohibited or must be used with caution because of their potential for metabolic interactions with SPR001. In all cases, if there is a question or concern about a specific medication being used by the subject, it is appropriate to review the usage with the Medical Monitor before enrolling the subject in the study. If a medication is to be washed out, it should be stopped at least 30 days or 5 half-lives, whichever is longer, before the first dose of SPR001 in this study and cannot be resumed until after the safety follow-up visit. In many cases, washout will necessitate rescreening. If a prohibited medication such as an antibiotic or antifungal agent is required during a subject's study participation, the Medical Monitor should be consulted to discuss appropriate actions, such as the temporary withholding of SPR001 until treatment with the prohibited agent is completed.

#### 6.5.2.1 Prohibited Concomitant Medications

Other investigational drugs are prohibited during the study.

Rosiglitazone treatment is prohibited during the study because it could affect the subject's ACTH levels. Treatment with testosterone is also prohibited. In general, subjects who require ongoing treatment with rosiglitazone or testosterone should not be screened.

In vitro cytochrome P450 (CYP) reaction phenotyping has indicated that SPN001 is metabolized by CYP3A4. Therefore, drugs that are known strong inducers or inhibitors of CYP3A4 are generally prohibited during the study and require a washout period before screening. Stable daily doses of glucocorticoids and birth control are not restricted.

Specifically prohibited concomitant medications are listed in [Section 12.1.1](#).

#### ***6.5.2.2 Concomitant Medications of Concern***

In vitro metabolism studies have indicated that SPN001 has the potential to inhibit CYP3A4, 2C8, 2C9, and 2C19. Therefore, drugs metabolized by CYP3A4, 2C8, 2C9, and/or 2C19 should be avoided or used with caution, especially drugs that are sensitive substrates of these enzymes or that have narrow therapeutic ranges. Sensitive CYP substrates are drugs whose plasma area under the curve (AUC) has been shown to increase  $\geq 5$ -fold when co-administered with a known CYP inhibitor and drugs for which the AUC in poor metabolizers is  $>5$ -fold the AUC in extensive metabolizers. Drugs with narrow therapeutic ranges are those for which even small increases in a subject's exposure to these drugs (potentially induced by the concomitant use of the CYP inhibitor SPR001) could lead to serious safety concerns (e.g., torsades de pointes).

Whenever feasible, subjects will discontinue use of a medication of concern and undergo a washout period before screening. However, if washout is not feasible, the Investigator should consult with the Medical Monitor to decide on the best course of action. If a medication of concern is to be continued, it must be used with caution and the subject must be carefully followed.

Specific concomitant medications of concern are listed in [Section 12.1.2](#).

It is important to note that many commonly used medications are listed as drugs of concern, including certain statins (lovastatin, simvastatin), anti-inflammatory agents (celecoxib, felodipine), migraine remedies (ergotamine, dihydroergotamine, eletriptan), anxiolytics (buspirone, clobazam, midazolam), and drugs for erectile dysfunction (avanafil, sildenafil, vardenafil). Subjects must be willing to refrain from the use of these erectile dysfunction drugs during the study. It is critical that each subject's concomitant medications are carefully compared to the list.

## 7 DOSE REDUCTION, STUDY DRUG DISCONTINUATION, AND PARTICIPANT WITHDRAWAL

### 7.1 Dose-Limiting Toxicity and Dose Reduction

A DLT is defined as a Grade 3 or higher TEAE considered at least possibly related to study drug. If a subject experiences a DLT, the Investigator may reduce the subject's daily dose of SPR001 (by 50 to 200 mg), depending on the TEAE, in order to keep the subject on study. A Grade 3 or higher TEAE considered related to study drug will also be considered an AESI (see [Section 8.2.8](#)). Potential dose reductions must be discussed with the Medical Monitor. At any time during the study, subjects who experience any clinically significant signs of acute adrenal insufficiency (e.g., postural hypotension, nausea, abdominal pain) may have their study drug dose reduced or withheld and/or their glucocorticoid replacement therapy modified (see [Section 7.2.4](#)).

### 7.2 Study Drug Discontinuation

Subjects may voluntarily discontinue study drug or the Investigator may discontinue a subject's study drug at any time. Investigators should discuss any safety concerns with the Medical Monitor as soon as possible to determine whether a subject should continue or discontinue study drug. Study drug will be discontinued in subjects who experience clinically significant liver chemistry, QTcF, or other individual treatment stopping criteria described in this section. Subjects may discontinue study drug but remain in the study for follow-up.

[figure not shown]
If study drug is discontinued, the Investigator will report the discontinuation to the Medical Monitor, document the date and reason for study drug discontinuation on the appropriate electronic case report form (eCRF), schedule an early termination visit for the subject (see the Schedule of Activities in [Section 1.3](#)), provide or arrange for appropriate follow-up, and document the course of the subject's condition.

Subjects who prematurely discontinue study drug may be replaced at the discretion of the Sponsor to ensure adequate numbers of evaluable subjects.

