### **Dose, Route, Regimen**

Initial subjects who enroll in this study will be treated with oral study drug at 400 mg QD at 10pm for 12 weeks. This dose is within the range of doses that were well tolerated and reduced key hormones (ACTH, 17-OHP, and androstenedione) in subjects with CAH in Cohort A of Study SPR001-201. For subjects who enroll later on in this study, the dose strength may be increased or decreased (by no more than 2-fold) and/or the dose regimen may be adjusted (e.g., to BID dosing, a regimen being tested in Study SPR001-201). In general, subjects are expected to complete the study at the dose strength and on the dose regimen at which they started the study, unless they experience a clinically significant AE that would warrant a dose reduction. An SRC will review the available safety, PK, and PD data from Study SPR001-201 Cohorts B/C/D and from this study on an ongoing basis and provide recommendations to the Sponsor, who will ultimately decide on any dosing adjustments in this study.

Study drug will be taken with a meal or 5 to 15 minutes after consumption of a standardized snack. On the mornings of all study visits, including the screening visit, subjects should hold off on taking any morning glucocorticoid medication (and on taking study drug, if a morning dose is added and if applicable to the visit) until after laboratory assessments are completed. On all other days during the study, subjects should take any morning glucocorticoid medication (and morning dose of study drug, if applicable) at their usual time.

If a subject experiences a DLT (defined as a Grade 3 or higher treatment-emergent adverse event [TEAE] considered at least possibly related to study drug), the Investigator may reduce the subject's daily dose of SPR001 (by 50 to 200 mg), depending on the TEAE and upon discussion with the Sponsor's Medical Monitor. Study drug will be discontinued in subjects who experience clinically significant liver chemistry, QTcF, or other individual treatment stopping criteria ([Section 7.2](#)).

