## 7.2.3 Suicidality Stopping Criteria

SPR001 is considered to be a central nervous system (CNS)-active study drug. Some CNS-active drugs may be associated with an increased risk of suicidal ideation in certain populations. Although SPR001 has not been shown to be associated with an increased risk of suicidal thinking or behavior when given to healthy volunteers, subjects will be monitored for such events during this study using the C-SSRS (see [Section 8.1.6.1](#)).

Individuals who provide a positive answer to question 3, 4, or 5 of the C-SSRS (on suicidal ideation) at screening or baseline are not eligible for this study. The Investigator should immediately contact the Medical Monitor to discuss possible study drug discontinuation and appropriate safety follow-up for a subject who provides a positive answer to question 3, 4, or 5 of the C-SSRS at any visit after baseline. This will also be considered an AESI (see [Section 8.2.8](#)).

The subject's HADS score should also be evaluated in conjunction with the C-SSRS (see depression stopping criteria in [Section 7.2.5](#)).

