#### **7.2.4 Adrenal Insufficiency Stopping Criteria**

If a subject dosed with study drug exhibits clinically significant signs of acute adrenal insufficiency, such as postural hypotension, nausea, and abdominal pain, the Investigator should consider withholding the subject's dose(s) of SPR001, initiate appropriate corticosteroid therapy, and contact the Medical Monitor. If there is no clear explanation for the subject's acute adrenal insufficiency, such as inadequate corticosteroid replacement dosing or low circulating levels of plasma cortisol, the Investigator should review the subject with the Medical Monitor for possible study drug discontinuation.

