#### **7.2.5 Depression Stopping Criteria**

Individuals who score >12 on either the depression or anxiety subscale of the HADS (see [Section 8.1.6.2](#)) at screening or baseline are generally not eligible for this study. The Investigator should immediately contact the Medical Monitor to discuss possible study drug discontinuation and appropriate safety follow-up for a subject who scores >12 on either the depression or anxiety subscale of the HADS at any visit after baseline. This will also be considered an AESI (see [Section 8.2.8](#)). Reasons for an elevated HADS score (aside from clinical depression) include chronic pain and stress.

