#### **7.2.6 Reproductive Hormone Stopping Criteria**

Subjects with CAH can be expected to have abnormal reproductive hormone levels because deficient 21-hydroxylase enzyme activity leads 1) to elevated levels of cortisol precursors that are shunted into reproductive hormone biosynthetic pathways and 2) to low levels of the cortisol that normally provides negative feedback on the HPA axis. Standard-of-care therapy with glucocorticoid and mineralocorticoid replacement typically does not fully normalize adrenal steroid production pathways and signaling systems, including ACTH and CRF levels. Thus, subjects with CAH can be expected to have abnormal plasma concentrations of various androgens and progestogens at baseline. Therapy with an effective CRF receptor antagonist may in fact shift the balance between various intermediates in the steroid biosynthetic pathway.

If a subject experiences changes from baseline in reproductive hormone(s), the Investigator should contact the Medical Monitor to discuss whether such changes represent clinically significant reproductive abnormalities, potential risks to the subject, possible study drug discontinuation, and appropriate safety follow-up. These changes include but are not limited to significant changes in LH, FSH, inhibin B, SHBG, estradiol, prolactin, or progesterone; testicular dysfunction in men; and changes in menstrual cyclicity in women.

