#### **7.2.7 Potentially Clinically Significant Adverse Events**

Clinically significant AEs include but are not limited to SAEs ([Section 8.2.2](#)), AEs leading to study drug discontinuation/study withdrawal, DLTs ([Section 7.1](#)), and AESIs ([Section 8.2.8](#)) that are each considered at least possibly related to study drug. The occurrence of any clinically

significant AE will receive special consideration in decisions regarding continuation or suspension of dosing or enrollment and will be reported to the SRC within 1 day of awareness for immediate review.

Section 12.3 also provides a list of signs and symptoms (Section 12.3.1) and a list of laboratory findings (Section 12.3.2) that constitute potentially clinically significant AEs not otherwise specified among the foregoing individual treatment stopping criteria. These provide guidelines for a level of moderate-severe abnormality in safety findings that could cause harm to subject health and may preclude further study drug dosing. These lists are intended to guide the Investigator and are not meant to be a set of absolute criteria. Safety parameters not included in the list may be interpreted in a similar fashion according to Investigator judgment. Common Terminology Criteria for Adverse Events (CTCAE) severity grading should also be referenced (Section 8.2.3.1).

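### SAP 8.7 words HADS depression scoring opposite to the protocol, and the promised summary of adverse events of special interest is missing without explanation

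*Protocol*

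**What the plan says.** **HADS scoring.** Protocol 8.1.6.2 describes 14 items, seven each for anxiety and depression. Every item is rated 0 to 3 by how often symptoms occurred, with 0 for not at all and 3 for very often. SAP 8.7 keeps that direction for anxiety (3 is the maximum response) but gives depression the reverse (3 minimal, 0 maximal). It then summarizes anxiety, depression and total scores as continuous variables in Table 14.3.8.1. Protocol Section 3 lists changes in the HADS among the primary safety endpoints.

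**AESIs.** Protocol Section 3 names AESIs within the primary safety endpoint, and 9.3.5 commits to summarizing them. Section 8.2.8 defines four categories:
- C-SSRS ideation of type 3, 4 or 5;
- a high HADS score or other sign of worsening depression;
- significant liver chemistry changes short of the stopping rules;
- related treatment-emergent events of Grade 3 or higher.

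SAP 3.2.1 names only AEs and SAEs as event endpoints. SAP 5.1.1 declares three changes to protocol analyses (acne and hirsutism, semen, menstrual cyclicity), and AESIs are not among them.

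**Stopping wording.** Protocol 7.2 states: "Study drug will be discontinued in subjects who experience clinically significant liver chemistry, QTcF, or other individual treatment stopping criteria described in this section". The synopsis repeats the rule. Section 7.2.7 refers back to the earlier subsections with the words "not otherwise specified among the foregoing individual treatment stopping criteria". Within 7.2.3 to 7.2.6, however, discontinuation is only something to be discussed or reviewed.

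**The concern.** The HADS is one of the two instruments used to monitor mood and suicidality on a drug that protocol 7.2.3 treats as CNS-active. If a programmer follows SAP 8.7 as written, a worsening in depression appears as a falling score. A subject who worsens equally on both subscales shows no change in the total. A primary safety table would then be unreadable or misleading, with nothing on its face to show it.

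For AESIs, a reader of the summary tables would get no count for a named component of the primary endpoint and no statement that it had been dropped. The SAE tables cannot stand in, because protocol 8.2.8 defines AESIs as events that do not meet SAE criteria.

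The Section 7.2 wording raises a smaller question: does meeting the criteria in 7.2.3 to 7.2.6 mean stop, or review?

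**Working it through.** The plan states no figure to reproduce here. The check is a comparison of text plus the arithmetic of a reversed subscale.

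**1. HADS direction.** Inputs: seven depression items scored 0 to 3 (protocol 8.1.6.2 and SAP 8.7), so the subscale maximum is 7 × 3 = 21. Let A be the anxiety score and D the depression score in the protocol direction. Under the literal SAP wording each depression item becomes 3 minus its protocol value, so D′ = 21 − D and the total is A + 21 − D.

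| A | D | Protocol total A + D | Literal SAP total A + 21 − D |
|---|---|---|---|
| 0 | 0 | 0 | 21 |
| 13 | 13 | 26 | 21 |
| 21 | 21 | 42 | 21 |
| 21 | 0 | 21 | 42 |
| 0 | 21 | 21 | 0 |

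The change in D′ is minus the change in D, so worsening looks like improvement. The change in the total is the change in A minus the change in D, so equal worsening cancels.

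The protocol's alert level is a subscale score above 12 (7.2.5), that is D = 13 to 21. Under the literal wording those scores become 8 to 0. D′ > 12 means 21 − D > 12, so D ≤ 8. Each rule flags 9 of the 22 possible scores, no score is flagged by both, and D = 9 to 12 is flagged by neither. The SAP plans no such count. The point matters if one is added from SAP-scored data, or if someone compares the tabulated maximum with 12.

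**2. AESI output.** Places where an AESI entry could appear in the SAP:
- overall adverse event summary (SAP 8.1): 0 of 9 rows;
- Tables 14.3.3.1.1 to 14.3.3.6.1 (SAP 11.3): 0 of 11;
- Listings 16.2.7.1 to 16.2.7.5: 0 of 5;
- declared changes (SAP 5.1.1): 0 of 3.

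What can be recovered elsewhere, by category in protocol 8.2.8:
- C-SSRS ideation: Table 14.3.8.2.
- Related Grade 3 or higher events: drug-related events by severity, Table 14.3.3.3.2. This route largely covers dose-limiting toxicities too, which also lack a named table.
- Liver chemistry: shift Table 14.3.4.1.2.2 and Listing 16.2.8.2.1. The shifts are relative to the normal range.
- HADS: Table 14.3.8.1, whose format includes minimum and maximum, and Listing 16.2.6.3.

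None of these gives the number of subjects with at least one AESI. A mean does not reveal a single alert either. With assumed scores of 3 in ten subjects and 13 in one, it is (10 × 3 + 13)/11 = 3.9.

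**3. Stopping wording.** Of the six subsections 7.2.1 to 7.2.6, QT (7.2.2) requires discontinuation. Liver chemistry points to 12.2.1, which says to stop immediately, although under a heading of suggested actions. The other four are discretionary:
- 7.2.3: "possible study drug discontinuation and appropriate safety follow-up for a subject who provides a positive answer to question 3, 4, or 5"
- 7.2.4: "the Investigator should review the subject with the Medical Monitor for possible study drug discontinuation"
- 7.2.5: "to discuss possible study drug discontinuation and appropriate safety follow-up for a subject who scores >12 on either"
- 7.2.6: "potential risks to the subject, possible study drug discontinuation, and appropriate safety follow-up"

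**The case against.** **HADS.** SAP 8.7 speaks of a response, not of symptom severity. It may be describing raw answers to positively phrased items, and planning a total suggests that a common direction was intended. That is a fair reading. It stands as a reason not to assert that the scores will be reversed. It does not remove the conflict, because no recoding step is stated. A reader might also infer that subjects were wrongly screened or monitored. The documents do not support that: eligibility and post-baseline triggers rest on the protocol's scoring, not on SAP 8.7.

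**AESIs.** Counting places where the label is absent is not the same as counting missing events. AESIs are adverse events, so treatment-emergent ones recorded as such appear in the event tables and Listing 16.2.7.1. Most components can be read from other outputs, and with 11 subjects the listings can be linked by hand. This stands: it is a reporting gap, not lost data. A reader might go further and treat the missing count of HADS scores above 12 as a breach. It is not one, since protocol 9.3.5 promises only descriptive statistics for the HADS and the SAP provides them. Such a count is relevant only as part of the AESI summary.

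**Stopping wording.** A reader might infer that the protocol contradicts itself, or that continuing a subject with a HADS score above 12 violates it. Section 7.2 does not bear that weight. Its rule is qualified by clinical significance, and the sentence before it directs Investigators to consult the Medical Monitor "to determine whether a subject should continue or discontinue study drug". Each subsection then gives its own instruction. Decisions are not left unrecorded in general either: action taken is recorded for each event (8.2.3), AESIs go on the SAE Report Form (8.2.8), and clinically significant related events reach the safety review committee within a day (7.2.7). A decision to continue under 7.2.4 or 7.2.6 is the thinner case.

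**Conclusion.** Two SAP corrections should be made before the tables are produced.

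First, SAP 8.7 conflicts with protocol 8.1.6.2 on the direction of the depression items. The conflict in wording is certain. An actual reversal depends on the SAP being programmed literally with no recoding. In that case D′ = 21 − D, and the total is 21 at both extremes instead of 0 and 42.

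Second, the AESI summary promised in protocol 9.3.5 is absent from the SAP, and SAP 5.1.1 does not declare it dropped. The gap is one roll-up for 11 subjects, with most components visible elsewhere. SAP 5.1.2, on revisions to the plan, was not in the text available, so any statement there could not be checked.

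The stop-versus-review wording in protocol 7.2 is a minor clarification only. The documents give no frequency for any trigger, so no effect on discontinuation rates or on any safety conclusion is claimed.

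**What to change.** - **SAP 8.7:** state that all 14 HADS items are scored 0 for no symptoms to 3 for most symptoms, after recoding of any positively phrased items, before subscale and total scores are calculated. Cost: one sentence, plus a check of the program for Table 14.3.8.1.
- **SAP 8.1 and 11.3:** add an AESI row or short table giving the number of subjects with at least one AESI, by the categories in protocol 8.2.8, including HADS anxiety or depression above 12. Derive the HADS counts only after the first correction. Otherwise, declare the omission in SAP 5.1.1 with a reason. Cost: one small output from data already collected; SAP 11.3 already allows the index to be updated.
- **Protocol 7.2 and synopsis (optional):** confine the mandatory wording to the liver chemistry and QT criteria, and say that 7.2.3 to 7.2.6 trigger Medical Monitor review with a documented decision. Cost: two sentences and one added line. The SAP's final sample size of 11 suggests that enrollment is over. If dosing is also complete, this matters only for later protocols.
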